14.4 Analysis of Secondary Endpoints

Differences in residual viral transcription by MA exposure will be evaluated using multivariate negative binomial regression, as previously described.⁷⁴ Potential covariates will include age, gender, nadir CD4+ T cell count, pre-ART HIV RNA, recent CD4+ T cell count, timing of ART (estimated date of HIV infection to date of

ART initiation), duration of ART suppression, and other illicit use (stimulant or opioid exposure detected on qualitative urine measurement). Linear regressions will be used to associate MA concentrations with beta-PEA levels. For the RNA sequencing data, within-individual differential gene expression analyses will be performed for each tissue type (blood and lymph node) and for each cell type (Tcm CD4+ T cells or CD14+ monocytes). Genes and pathways will be filtered for those associated with changes in viral transcription using several pathway sources - e.g., Ingenuity Pathway Analysis (IPA),⁷⁵ KEGG,⁷⁶ MsigDB (Broad),⁷⁷ and Damian Chaussabel's immune modules.⁷⁸ Functional Annotate Network (FAN) will be built using Genes2FANs⁷⁹ and Cytoscape⁸⁰ to show the key functional network elements that are downstream of candidate genes. String (string-db.org) will be used to build protein-protein interaction networks from the differentially expressed gene lists. Finally, graph theory analysis⁸¹ will be used to identify the functional motifs of the network.

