SECONDARY OBJECTIVES	
 1. Identify differentially expressed genes and proteins in blood, before and after short-term MA administration. 2. Determine whether trace amine receptor 1 (TAAR1) signaling mediates observed effects of MA administration.
NUMBER OF PARTICIPANTS	N=10
PARTICIPANT SELECTION CRITERIA	
Inclusion Criteria:
 
 1. Willing and able to provide written informed consent 2. Male or female, age \geq 18 years and \leq 65 years 3. Laboratory confirmed documentation of HIV-1 infection. 4. Continuous therapy with a DHHS recommended/alternative combination ART for least 12 months (at least 3 agents) at study entry with no regimen changes in the preceding 12 weeks 5. Maintenance of undetectable plasma HIV-1 RNA below the limit of quantification for at least 12 months. Episodes of

	
single HIV plasma RNA 50-500 copies/ml will not exclude participation if subsequent HIV plasma RNA is below the limit of assay detection.
 
6. No plans to modify ART during the study period (146 days, or approximately 5 months)7. Participant and your partner(s) are willing to use two forms of contraception throughout the study period as well as up to 60 days after the last day of study completion8. Ability and availability to participate in the full 146 days of the study (approximately 5 month) and maintain the inclusion/exclusion criteria9. No current or prior history of methamphetamine (MA) use disorder by DSM-5 diagnostic criteria. Participants may have a prior history of taking prescription medications containing amphetamines-type stimulants such as Adderall® or Dexedrine® or Ritalin for the treatment of conditions such as attention deficit hyperactivity disorder as long as the participant has not taken these medications in the last 12 months or plans to take these medications during the entire study period.
--	---

Exclusion Criteria:

1. History of methamphetamine (“meth”) use disorder by DSM-5 diagnostic criteria using the 11-symptom checklist.
2. Evidence of MA use other than due to the administered oral methamphetamine study drug, based on urine, hair, or serum MA measurements collected at baseline and follow-up study visits.
3. Current use of prescription medications containing amphetamine-type stimulants (e.g., Adderall®, Dexedrine®, Ritalin, etc.) within the past 1 year.
4. Sensitivity or allergy to amphetamine-type stimulants

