
STATISTICS Primary Analysis Plan
	
[name] has expertise in epidemiology and biostatistics. Differences in residual viral transcription by MA exposure will be evaluated using multivariate negative binomial regression, as previously described. Potential covariates will include age, gender, nadir CD4+ T cell count, pre-ART HIV RNA, recent CD4+ T cell count, timing of ART (estimated date of HIV infection to date of ART initiation), duration of ART suppression, and other illicit use (stimulant or opioid exposure detected on qualitative urine measurement). Linear regressions will be used to associate MA concentrations with urinary \square-PEA levels. For the RNA sequencing data, within-individual differential gene expression analyses will be performed for each tissue type (blood and lymph node) and for each cell type (Tcm CD4+ T cells or CD14+ monocytes). Deconvolution of cell-specific gene signatures⁶⁹ will be performed to allow analysis of further cell subsets (e.g., “classical” vs. “non-classical” monocytes). For DNA variant analyses, SNP-based association tests between variants and TAAR1 signaling biomarkers will be performed using PLINK/SEQ, while gene-based association tests will be performed using SKAT-O, which aggregates variants across a region and assesses whether the number of variants with non-zero effect sizes within that region exceeds that of chance expectation. Genes and pathways will be filtered for those associated with changes in viral transcription using several pathway sources - e.g., Ingenuity Pathway Analysis (IPA), KEGG, MsigDB (Broad), and Damian Chaussabel’s immune modules. Functional Annotate Network (FAN) will be built using Genes2FANs and Cytoscape to show the key functional network elements that are downstream of candidate genes. String (string-db.org) will be used to build protein-protein interaction networks from the differentially expressed gene lists. Finally, graph theory analysis will be used to identify the functional motifs of the network.

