In support of prior *ex vivo* and animal data demonstrating a link between MA exposure and viral transcription and immune activation, we recently studied 55 HIV+ ART-suppressed participants¹⁵ who use MA and observed that recent MA use was associated with significant changes in the expression of genes associated with HIV latency (*FCGR2A*, encoding CD32a¹⁶ and *PDL1*, encoding the immune exhaustion marker, programmed cell death-1 ligand¹⁷), as well as genes involved in cell cycle regulation (*FOXO4*¹⁸, *RBM38*¹⁹, *MAPK2*²⁰). MA use was also associated with changes in innate immune activation/antigen presentation and inflammation (JAK-STAT signaling) pathways, consistent with prior experimental data demonstrating that MA exposure influences immune activation^{10,12,21} and pro-inflammatory cytokine release.^{22,23} Although findings from this cross-sectional study support the scientific premise of the proposed study, experimental models are needed to better characterize the mechanisms whereby acute MA exposure alters multiple biological pathways relevant to HIV persistence at the cellular level. As such, the goals of this study are to identify potential interventional targets for future HIV eradication strategies. For example, we will also specifically investigate a clinically promising target for the treatment of psychostimulant addiction,²⁴⁻²⁶ trace amine-associated receptor 1 (TAAR1) signaling, and a mechanism by which MA may induce PKC activation and viral transcription.^{27,28}

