host genetics plays an important role in determining MA addiction, the underlying mechanism by which MA induces immune effects and promotes viral production is still incompletely understood. Our data will contribute important DNA, RNA, and protein level data to current public databases that aim to annotate putative regulatory function and tissue-specific regulatory genetic effects.⁴⁵⁻⁴⁷ The proposed study will use these combined methods to investigate potential direct and indirect effects of MA on viral transcription (possibly mediated by TAAR1) and inflammation in HIV+ ART suppressed individuals.

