3.2 Secondary Objectives

The second objective is to identify differentially expressed genes and proteins in blood, before and after short-term MA administration.

The third objective is to determine whether trace amine receptor 1 (TAAR1) signaling mediates observed effects of MA administration.

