9.3.3 Immunophenotyping

We will measure the host and viral transcriptome pre- and post-dosing by performing RNA sequencing (RNA-seq) on isolated CD4+ T-cells and applying validated bioinformatic pipelines for gene expression analysis. Transcriptomic profiling of longitudinal samples will enable characterization of the effects of oral methamphetamine on host gene expression. In addition, consideration of the gene expression data within the context of the aforementioned virologic measurements will allow us to identify specific host transcriptomic correlates of viral reactivation. We hypothesize that the expression of

particular genes (NFkB pathway components, cell-cycle regulators, cell-intrinsic immune factors) will be associated with the degree of viral reactivation.

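### The TAAR1 mediation objective is not matched by the analysis plan: beta-PEA is analysed against methamphetamine concentration and DNA variants, but never against a viral or immune outcome

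*Combined protocol and SAP*

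**What the plan says.** Section 3.2 gives as the third objective to "determine whether trace amine receptor 1 (TAAR1) signaling mediates observed effects of MA administration", and the synopsis repeats it as the second of its secondary objectives. The background explains the interest. Section 1 presents TAAR1 signalling as "a mechanism by which MA may induce PKC activation and viral transcription", and Section 1.2 speaks of "potential direct and indirect effects of MA on viral transcription (possibly mediated by TAAR1) and inflammation".

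The synopsis lists TAAR1 metabolite production as a secondary endpoint. Section 9.3.8 measures it as beta-PEA in urine, with other trace amines still in assay development.

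Two planned analyses use this biomarker:

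- Section 14.4: "Linear regressions will be used to associate MA concentrations with beta-PEA levels". The synopsis statistics section has the same regression.
- Synopsis only: "SNP-based association tests between variants and TAAR1 signaling biomarkers will be performed using PLINK/SEQ", with companion gene-based tests.

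Two others concern viral outcomes and gene expression. In Section 14.4 and the synopsis, "Genes and pathways will be filtered for those associated with changes in viral transcription". Section 9.3.3 says that combining expression data with the virologic measurements "will allow us to identify specific host transcriptomic correlates of viral reactivation".

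The outcome models are in Section 14.3 (activation markers, cytokines, CA-US RNA and plasma HIV RNA, before and after study drug) and Section 14.4 (viral transcription by MA exposure, with a list of potential covariates). Beta-PEA appears in none of them.

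**The concern.** Mediation is a claim about a path: MA changes TAAR1 signalling, and that change in turn alters the viral or immune outcome. To address it, some analysis must hold the biomarker and the outcome together. The plan covers the first step only, and a positive result there is compatible with no mediation at all. For example, MA could raise beta-PEA and, by an unrelated route, raise CA-US RNA. Both planned analyses would then be positive.

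At stake is a stated secondary objective. It would either go unanswered or be answered by an analysis chosen after the data are seen.

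**Working it through.** **1. Which analyses contain what.** Setting the planned analyses side by side:

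| Planned analysis | Where | TAAR1 biomarker | Viral or immune outcome |
|---|---|---|---|
| MA concentration with beta-PEA | 14.4, synopsis | yes | no |
| DNA variants with TAAR1 biomarkers | synopsis | yes | no |
| Activation markers and cytokines, before and after drug | 14.3 | no | yes |
| CA-US RNA and plasma HIV RNA, before and after drug | 14.3 | no | yes |
| Viral transcription by MA exposure, with covariates | 14.4, synopsis | no | yes |
| Gene and pathway filter | 14.4, synopsis | not named | yes (viral) |
| Host transcriptomic correlates of viral reactivation | 9.3.3 | not named | yes (viral) |

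Of the 2 analyses that use the biomarker, 0 contain a viral or immune outcome. Of the 5 that contain such an outcome, 0 name the biomarker. No indirect effect or mediator-adjusted MA effect is described. The first step is also regressed on MA concentration rather than on randomised treatment, and Section 14.4 does not say whether placebo-period values enter.

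**2. The plan's own figure.** No sample-size figure is given for the TAAR1 objective. The only one for a viral outcome is in Section 14.5: n = 10, SD 0.6 log10, alpha 0.05, about 80% power for 0.5–0.6 log10. With a two-sided paired t test on 9 df, the noncentrality is d/SD × √n:

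- d = 0.6: 0.6/0.6 × √10 = 3.16, power 80.3%.
- d = 0.5: 0.5/0.6 × √10 = 2.64, power 65.1%.

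A one-sided test reaches 80% at 0.51. The stated range therefore reproduces across standard variants if 0.6 is read as the SD of the within-person change. It is not in dispute here.

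**3. What a linking analysis could show.** This measures the precision of the remedy, not the size of the gap. Inputs are n = 10 (14.5), two periods (4.1) and alpha 0.05, taken as two-sided. One value per participant per period and all correlations are assumed.

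- Residual df: 20 values − 10 participant effects − treatment − period − beta-PEA = 7.
- Partial correlation needed for p < 0.05: 2.365/√(2.365² + 7) = 0.67.
- Power by simulation (40,000 runs, MA-minus-placebo differences on intercept, sequence and beta-PEA difference): 12%, 29% and 62% at true partial correlations of 0.3, 0.5 and 0.7. Power reaches 80% at about 0.79 (100,000 runs). The sequence split hardly matters: 2/8 gives 12%, 29% and 61%.
- With 8 completers (5 df): 2.571/√(2.571² + 5) = 0.75 needed; power 10%, 21% and 46%.
- Median 95% half-width with no true association, n = 10: 0.83 outcome SD per SD of beta-PEA difference. If the SD of the MA-minus-placebo difference in CA-US RNA is 0.6, this is 0.83 × 0.6 = 0.50 log10. If 0.6 is the SD of one period's change and the periods are independent, the SD is 0.6 × √2 = 0.849, and the half-width is 0.83 × 0.849 = 0.70 log10.

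**The case against.** Four arguments count on the other side.

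- **The declared endpoint is analysed.** It is metabolite production, and that is regressed on MA concentration. This stands. A reader might infer that the TAAR1 endpoint has no analysis, and the documents do not support that. What is unmatched is the objective's wording about mediation.
- **The pathway work bears on the question.** The synopsis runs the variant tests, then the viral-transcription filter, then network building, so TAAR1-linked genes could pass through. This is relevant exploratory work. But a filter selects genes and does not estimate how beta-PEA relates to an outcome, and Section 9.3.3 names NF-κB components and other gene classes but no TAAR1 measure.
- **Ten participants cannot establish mediation, and an added regression would not either.** Correct. An unmeasured common cause could produce the same beta-PEA association. This is why rewording the objective comes first and the model is labelled exploratory. Low power is not itself a fault in the plan, which makes no power claim for this objective.
- **The missing schedule may settle the sampling.** Section 9.3.8 gives no urine times for beta-PEA, and those in Section 9.3.6 are for toxicology. A reader might infer that the samples are not taken. That cannot be concluded, because the Study Events Table was not supplied. A visit schedule would not, however, supply the missing analysis.

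**Conclusion.** The mismatch is real and limited. The plan promises to determine whether TAAR1 signalling mediates the MA effects, and no planned model relates beta-PEA to a viral or immune outcome. That conclusion rests on reading the text, takes the TAAR1 signalling biomarkers in the synopsis to be beta-PEA and related amines, and needs no numerical assumption.

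A reader might infer that the main comparison or safety is weakened. Neither uses beta-PEA, so neither is affected. A reader might also infer that one extra model would let the trial settle mediation. It would not: an interval half-width of about 0.50 to 0.70 log10 is about as large as the effect the trial is sized for, given the assumed SDs, and beta-PEA is not randomised. The point is worth correcting before unblinding because it is cheap and the analysis can still be prespecified.

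**What to change.** 1. In Section 3.2 and the synopsis, change the objective from determining to exploring whether TAAR1 signalling mediates the effects.
2. In Section 14.4, add one prespecified exploratory analysis using both periods:
   - the MA-versus-placebo effect on beta-PEA;
   - within-participant change in log10 CA-US RNA on treatment, period and change in beta-PEA, with a participant effect.

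   Report the beta-PEA coefficient with its 95% interval, and the treatment coefficient with and without beta-PEA. If beta-PEA rises in nearly everyone on MA, the adjusted treatment coefficient extrapolates to no rise and should be read with care.
3. State that beta-PEA is not randomised, so mediator–outcome confounding cannot be excluded, and that a null result does not rule mediation out.
4. Confirm the beta-PEA urine times. If the Study Events Table does not provide pre- and post-dose urine for beta-PEA in both periods, use post-dose values or make only the change in item 1.

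The cost is protocol and SAP wording plus one small analysis. No new samples are needed if the schedule already has the urine. Rewording alone costs nothing. The drawback is a wide interval that may be over-read, which item 3 is meant to prevent.

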14.5 Sample Size

Assuming a log normal distribution of HIV-1 cell-associated (CA)-US RNA and a standard deviation of 0.6 log₁₀ copies/10⁶ CD4+ T cells (as above for Aim 1125), with 10 participants in the treatment arm, and a null hypothesis of no change in CA-US RNA, we estimate that the study will have approximately 80% power to detect a 0.5-0.6 log₁₀ difference in CA-US RNA before and after treatment peak, at the 0.05 significance level. For the gene expression analyses, assuming a coefficient of variation of 0.32 and approximately 80-90% sequencing depth between 5 to 8 copies per base, respectively, we estimate having greater than 80% power to detect a two-fold change at the 0.05 significance level.

15 DATA COLLECTION, RETENTION AND MONITORING

15.1 Data Collection Instruments

The Investigator will prepare and maintain adequate and accurate source documents designed to record all observations and other pertinent data for each participant treated with the study drug.

Case report forms (CRFs) will be provided for each participant. Study personnel will enter data from source documents corresponding to a participant's visit into the protocol-specific paper CRF when the information corresponding to that visit is available. Participants will not be identified by name in the study database or on any study documents to be collected by the study investigators, but will be identified by a four-digit patient identification number (PID). If a correction is made on a CRF, the study staff member will line through the incorrect data, write in the correct data and initial and date the change.

The Principal Investigator is responsible for all information collected on participants enrolled in this study. All data collected during the course of this study must be reviewed and verified for completeness and accuracy by the Principal Investigator. A copy of the CRF will remain at the study site at the completion of the study.

15.2 Data Management Procedures

All data for our proposed study will be managed by the UCSF Data Coordinating Center, which is housed in the Department of Epidemiology and Biostatistics. This center currently serves 25 multicenter cohort and randomized trials throughout the world

The UCSF Department of Epidemiology and Biostatistics complies with federal, state, University, and campus electronic information security requirements through a combination of physical, technical, procedural, and management controls. At the procedural level, all Coordinating Center (CC) personnel sign a confidentiality agreement and undergo security awareness training for HIPAA and the handling of sensitive data. All employees of the University of California, San Francisco were required to obtain Security Awareness Training and implement appropriate security measures. New employees who use computers must take this training. Remote users of the data also receive training from the Data Management Group prior to gaining access to data systems.

15.3 Data Quality Control and Reporting

After data have been entered into the study database, a system of computerized data validation checks will be implemented and applied to the database on a regular basis. Query reports (Data Clarification Requests) pertaining to data omissions and discrepancies will be forwarded to the Investigators and study monitors for resolution. The study database will be updated in accordance with the resolved queries. All changes to the study database will be documented.

15.4 Archival of Data

The database is safeguarded against unauthorized access by established security procedures; appropriate backup copies of the database and related software files will be maintained. Databases are backed up by the database administrator in conjunction with any updates or changes to the database.

The network at UCSF CC is privately maintained, hardware firewalled and none of the workstations or database servers can be directly addressed from outside the Local Area Network. Website communications are encrypted using an SSL certificate. Network OS is Windows Active Directory. Remote access is via SSL-VPN. A network administrator and server administrators support the network and servers and the Data Systems Services Group (developers/database administrators) support the database and web applications. The support team is paged 24/7 when servers or critical data center equipment experiences issues.

All study data is housed at the UCSF CC in a secure server room. The building is locked outside of normal business hours. All system servers are located in a limited access suite fitted with an Access Control System. Within the locked suite is a locked server room fitted with an additional secure door. Only critical Information Systems staff possesses the access code required to enter the room. All who enter the system server room must sign a server room access log in accordance with UCSF CC IT Security SOPs.

Study database access is controlled via two-factor password security. Development workstation access is controlled via Microsoft logon. Once a workstation is accessible,

access to the study data on the SQL server via any development application requires appropriate logon-specific permission assigned in SQL Security Manager. Communication between study servers and client machines on the UCSF network are encrypted using an SSL certificate. All servers are protected from viruses by McAfee VirusScan. This software automatically checks for virus signature file updates from a McAfee FTP site once an hour, and if necessary directly updates itself. All anti-virus software is monitored and network personnel notified in the event that the software stops functioning on a given server.

All study data are stored on SQL servers managed by the UCSF Coordinating Center. All servers are housed in a secure server room.

Web site access: The study web sites are protected by two hardware-based firewalls to shape incoming and outgoing traffic. Access to the study management web site is restricted to approved personnel only. Approved personnel gain access to the system using a multi-layered authentication scheme. A log of all personnel with level of access is kept and updated regularly. Once a clinic site user accesses the system they are only permitted to view data received from their site, with the exception of official aggregate reports. Users are not permitted to view or alter another clinic's data.

Data transmission from web server to client: The UCSF CC currently utilizes Secure Socket Layer (SSL) protocol which protects all data transmission sent over the Internet between the CC IIS Web Server and every client machine which accesses our study web sites.

System Backup

Back-ups: All department workstations and servers are automatically backed-up every night. Back-up systems are monitored daily.

Failover Site: As part of the nightly database maintenance procedures, all SQL databases are backed up to a "failover" site at our co-location facility. This site has copies of the study databases as well as all associated systems required to carry on a study in the event of a disaster at the primary location.

Off-site Storage: Network back-ups are written to tape and sent to an off-site vendor every two weeks, with tapes being rotated every two months.

Recovery/File Restores: If important files or data from the network are accidentally deleted, the IT staff can locate the items and restore data within an hour in most cases.

